
Title: Mechanisms and Phenotypes of Hypertension in Patients in Chronic Hemodialysis
 
Justification. Cardiovascular complications associated to arterial hypertension are critical determinants of the mortality of patients in chronic hemodialysis. Identification of the activity of the renin-angiotensin system and immune reactivity in association with water overload is of clinical importance because they are potentially treatable.
 
Aims. To examine systemic arterial blood pressure ambulatory blood pressure monitoring (ABPM) in the interdialytic period and its relation to the activity of the renin angiotensin system, immune reactivity and interdialytic weight gain in patients in chronic hemodialysis.
 
General design. Prospective study of a cohort of patients in the chronic hemodialysis program in the Instituto Nacional de Ciencias Médicas y Nutrición Salvador Zubirán. Patients with the inclusion criteria will be evaluated with ABPM during the 24 hours in the interdialytic period. Weight, blood pressure, dialysis characteristics will be recorded. Blood samples will be obtained for hormonal determinations and immune reactivity at the end of the interdialytic period. Ultrasound will be used for determination of cardiac output and central venous pressure. Systemic vascular resistance will be calculated. Electric bioimpedance will be obtained would be obtained the first post dialysis day of the long interdialytic interval. *
	

 • Note: bioimpedance was not obtained and was not part of the study 	
Background.	

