The purpose of the study is to evaluate factors that may importantly contribute to hypertension in chronic dialysis patients; in particular, the renin-angiotensin system (RAAS), the sympathetic nervous system and inflammatory immune reactivity. In relation to the RAAS, Neuman et al.²¹, found that basal levels of angiotensin II are higher in patients with CKD than in normal controls, but the reduction resulting from volume expansion is normal, indicating that physiologic responses are normal. We also know from the studies of Shalekamp et al.²² that the activation of the renin-angiotensin system in CKD is not uniform and there are patients with normal and patients with high renin activity. In relation to inflammatory reactivity generated by autoimmune mechanisms, studies of several groups including ourselves^{6,7,23,24} have established the inflammation in the arterial wall, in the central nervous system and in the kidney play an important pathogenic role by reducing vasodilatory responses that may be corrected with T regulatory cells²⁵, increasing the activity of the sympathetic nervous system²⁶⁻²⁸, inhibiting pressure natriuresis²⁹ and stimulating sodium reabsorption^{30,31}. If these findings are shown in dialysis patients it is possible that anti-inflammatory treatment could have anti-hypertensive effects as it has been shown in experimental models and in patients³².

An important aspect is the relationship between interdialytic weight gain and the phenotypes of arterial hypertension (sustained hypertension, diurnal and nocturnal hypertension, normal nocturnal dipping, non-dipping, exaggerated dipping and reverse dipping) that may be evaluated with ambulatory blood pressure monitoring (ABPM)³³ that are associated with worse prognosis^{34,35}. Of interest, there are significant differences between ABPM and pre and post-dialysis blood pressure that are worthy to examine. and there is a high incidence of non-dippers in patients with CKD³⁶ and in patients with inflammation³⁷⁻³⁹.

Hypothesis and research questions.

What is the relative importance of the renin-angiotensin system, the inflammatory immune reactivity and water overload in the interdialytic blood pressure in dialysis patients?

Working hypothesis: In patients in chronic dialysis the activity of the renin-angiotensin system and the inflammatory reactivity play a critical role in the severity of hypertension and in the absence of nocturnal dipping of blood pressure

Outcomes.

Primary Outcome :

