Determine the relationship of blood pressure determined by ambulatory monitoring (ABPM) in the interdialytic period and the interdialytic weight gain and the levels of angiotensin II and inflammatory markers in patients in chronic dialysis.

Secondary Outcomes:

- 1) Determine the relationship of other parameters relevant to blood pressure pathophysiology with interdialytic weight gain and blood pressure
- 2) Evaluate the relationship between interdialytic weight gain, and other variables under study with hemodynamic parameters (systemic vascular resistance and cardiac output).
- 3) Evaluate differences between ABPM and dialysis blood pressure.

Methods. .

General

- Design of the study: One cohort. Observational prospective study.
- Patients: Patients in the chronic hemodialysis program in the Instituto Nacional de Ciencias Médicas y Nutrición “Salvador Zubirán” that meet the inclusion criteria and sign informed consent
- Date. abril 2023– junio 2024

- Days and hemodialysis and hemodialysis prescription will not be modified in the study. .
- Ambulatory blood pressure monitoring will be started after dialysis when the patient will be fitted with the equipment for ambulatory blood pressure monitoring and receive the instructions for its use.
- Blood samples (10 ml) will be taken at the end of the interdialytic period, (prior to the next dialysis) for the biomarkers under study.
- 1-2 hours after the end of dialysis the determination of cardiac output and central venous pressure determinations for calculation of the peripheral vascular resistance will be done by experts with experience in ultrasound methodology.

Methods

Hemodynamic determinations. Cardiac output will be measured by experts with experience by transthoracic echocardiography using ultrasound equipment Siemens Acuson P500 with convex transducer of 2-5Mhz and lineal transducer of 7.5Mhz. Measurements will be done in the 4th intercostal space at the mid clavicular line. Cardiac output (systolic volume x heart frequency) will be determined by ultrasound doppler of the flow of the outlet of left ventricle and the aortic area.

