Ambulatory blood pressure monitoring will be done with Space Lab ambulatory monitor (SpaceLabs Co) with cuffs appropriate for the patient's size starting after dialysis. Measurement will be programmed to be taken every 30 minutes during the day and every hour when the patient goes to bed. The patient will bring the equipment to the hospital when he comes for the next dialysis.

Biometric Bioimpedance. It was impossible to coordinate bioimpedance determinations within one week of the studies and this part of the study was omitted.

Blood samples and laboratory determinations. Blood samples (10 ml) will be taken from the venous side of the vascular access before the beginning of dialysis (end of the interdialytic period) and allowed to coagulate at 2-4°C. Serum samples will be stored at -80°C until the time of assay. All determinations will be done in the research laboratory of the Dept. of Nephrology and Mineral Metabolism of the Instituto de Ciencias Medicas y Nutrición "Salvador Zubirán". Angiotensin II will be determined by ELISA (my BioSource Cat.# MBS703599); Norepinephrine by ELISA (ABCAM, Cat. # AB287789); Copeptin by ELISA (Biotechne/NovusBiological, Cat, # NBP2-69822), TNF α by ELISA (Human TNF-alpha Quantikine HS ELISA, R&D systems, Cat.# HSTA00E). All laboratory determinations will be done following the instructions of the commercial supplier. Peripheral white cell counts were used to calculate the NMLR (neutrophils + monocytes /lymphocytes ratio) inflammation index.

Informed Consent.

Presented separately

Medical Intervention

None. Is an observational study.

Sample size

All the patients in the chronic hemodialysis program of the INCMNSZ that meet the inclusion criteria will be invited to participate.

Inclusion criteria

- 18 years of age or older
- More than 3 months in chronic dialysis
- Stable clinical conditions with no evidence of infection or treatment changes in the previous month

- Signed informed consent to participate in the study.

Exclusion Criteria

- Previous nephrectomy
- Participation of the patient in another clinical trial requiring interventional treatment
- Patients with prosthesis and pacemakers
- Incapacity of placement of ABPM or insufficient valid recordings
- Incomplete collection of data
- Voluntary withdrawing of informed consent

Statistical Analysis. .

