Gaussian (normal) distribution will be evaluated with Kolmogorov-Smirnoff tests. Data will be expressed with mean and standard deviation or standard error of the mean and 95% confidence interval. Variables with not normal distribution will be expressed with median and interquartile range. Categorical variables will be expressed as frequencies and percentages. Comparisons between two groups with normal distribution will be done with t tests and between several groups with one way ANOVA with Tukey post-tests. Comparisons in groups that do not have a normal distribution will be done with Kruskal-Wallis tests. Correlations will be explored with Pearson (data with normal distribution) or Spearman (data with not normal distribution). Normality of log2 data distribution will be explored when obtained data do not fit with a normal distribution. Statistical calculations will be done with software STATA (Statistic Data Analysis version 14.1 or with Graphpad 10 program. Two-tail p values <0.05 will be considered significant.

Groups.

There is one population of patients and for the purpose of some analyses, patients will be categorized in 3 groups by their mean ambulatory systolic blood pressure (ABP-SBP) : 1. ABP-SBP <130 mmHg (normotensives); 2) ABP-SBP 130-139 mmHg (prehypertensives) and 3) ≥140 mmHg (hypertensives)

Mechanisms for assignation of treatments.

There will be no treatment assigned as part of the study

Recruitment potential

We aim to recruit all patients that meet the inclusion criteria. Our estimate is 40-45 patients from a total of 50-55 in the chronic hemodialysis program of the INCMNSZ.

Recruitment incentives.

There will be no incentives.

Therapy

There will be no therapy as part of the study. Treatment received by the patient will not be modified.

Retirement of participants

Premature retirement of a participant could occur at the patient's request or by the unexpected development of fever or adverse event during the study. Cause of retirement will be duly recorded

Samples, administration and monitoring of the study.

Samples will be used only for the purposes of the study. The study will be conducted or supervised by one of the investigators. Any adverse event will be immediately notified to the treatment physician.

Investigates will meet every month to discuss the progress of the study.

Methods of contacting the participants

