# **MECHANISMS AND PHENOTYPES OF HYPERTENSION IN PATIENTS IN CHRONIC HEMODIALYSIS**

**NCT06764277**

**DATE: 09/11/2025**

**STATISTICAL ANALYSES**

### **Statistical analyses.**

All statistical analyses will be performed using GraphPad Prism version 10. The normality of data distributions was assessed using the Kolmogorov–Smirnov test. For comparisons between two groups, unpaired Student's t-tests will be applied when data followed a normal distribution, and the Mann–Whitney U test will be used for non-normally distributed data. For comparisons among more than two groups, one-way analysis of variance (ANOVA) will be performed for normally distributed data, followed by Tukey's post hoc test. When data did not meet normality assumptions, the Kruskal–Wallis test will be used, followed by Dunn's post hoc test for multiple comparisons.

For all analyses, two-tailed p-values  $< 0.05$  will be considered statistically significant. The assumptions underlying parametric tests (normality and homogeneity of variances) will be verified prior to analysis; if assumptions were not met, appropriate non-parametric alternatives will be used as described above.

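### Does the missing averaging rule for mean ambulatory systolic pressure put the three-group comparison at risk?

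*Protocol*

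**What the plan says.** In the Protocol, Methods, the ambulatory monitoring paragraph sets the reading schedule: "Measurement will be programmed to be taken every 30 minutes during the day and every hour when the patient goes to bed". The abstract gives the window: "Patients with the inclusion criteria will be evaluated with ABPM during the 24 hours in the interdialytic period". The Groups section then says "patients will be categorized in 3 groups by their mean ambulatory systolic blood pressure (ABP-SBP"), with cut-points at 130 and 140 mmHg, and limits the grouping to some of the analyses. No weighting is given there or elsewhere in the protocol.

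The SAP does not mention ambulatory monitoring or the groups by name. It describes group comparisons only: "For comparisons among more than two groups, one-way analysis of variance (ANOVA) will be performed for normally distributed data", with Kruskal–Wallis as the alternative. Correlations appear only in the protocol's Statistical Analysis section. The protocol's Background expects the day–night pattern to vary between patients, listing "normal nocturnal dipping, non-dipping, exaggerated dipping and reverse dipping". It also says that non-dipping is frequent in chronic kidney disease, without giving a figure.

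**The concern.** When readings are twice as dense by day as in bed, the word mean has two ordinary meanings that give different numbers. A plain average of readings leans towards daytime. It is higher than the time-weighted 24-hour mean in patients whose pressure falls at night, and lower in those whose pressure rises.

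Three features of this study make that look important. Groups are formed at fixed cut-points, so a shift of 1 or 2 mmHg can move a patient. The protocol expects only 40 to 45 patients, so each group is small. And the direction of the shift depends on nocturnal dipping, which is part of the working hypothesis. If the rule were chosen after the results were seen, group membership could be steered. The same mean might also enter the secondary outcome "Evaluate differences between ABPM and dialysis blood pressure", although the protocol does not say that an overall ambulatory mean is used there.

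**Working it through.** The documents give no value of this mean, so there is no stated figure to reproduce.

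**Inputs from the protocol.** Two readings per hour by day and one per hour in bed; a 24-hour window; cut-points at 130 and 140 mmHg; 40 to 45 patients expected (42 used below).

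**Assumptions, not in the documents.** 16 h up and 8 h in bed (range 14 to 17 h up); day systolic mean 135–145 mmHg, SD 15–20; night-time dip mean 5%, SD 8%; within-period reading SD 12 mmHg; no missing readings.

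**Weights.** With d day hours and b bed hours:

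- Plain mean, day weight = 2d/(2d + b) = 32/40 = 0.800.
- Time-weighted mean, day weight = d/(d + b) = 16/24 = 0.667.
- Plain minus time-weighted = 0.133 × (day − night systolic). The multiplier is 0.154 with 14 h up and 0.121 with 17 h up.

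**One patient, day systolic 140.**

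| Night-time change | Day − night (mmHg) | Shift in mean (mmHg) |
|---|---|---|
| 5% fall | 7 | +0.9 |
| 10% fall | 14 | +1.9 |
| 20% fall | 28 | +3.7 |
| 10% rise | −14 | −1.9 |

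A patient close to a cut-point can cross it. Day 143 and night 130 give (32×143 + 8×130)/40 = 140.4 plain and (16×143 + 8×130)/24 = 138.7 time-weighted. Day 127 and night 137 give 129.0 and 130.3.

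**Cohort.** In simulation under the assumptions above, the mean shift is 0.9 to 1.0 mmHg. Before reading noise, 5.2% to 7.0% of patients change group. With reading SD 12 the figure is 5.5% to 7.4%, or 0.055 × 42 = 2.3 to 0.074 × 42 = 3.1 patients. Other assumed distributions, with mean day–night differences from 0 to 14 mmHg, give about 2.5% to 10%, or roughly 1 to 4 patients of 42.

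**Effect on correlations.** The two means correlate at 0.995 to 0.997. A marker with r = 0.30 against the time-weighted mean has this r against the plain mean:

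- 0.303–0.306 if the marker is unrelated to dipping;
- 0.275–0.281 if its correlation with dipping is −0.30;
- 0.325–0.338 if its correlation with dipping is +0.30.

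The largest change is 0.038. At n = 42 the standard error of a correlation on the Fisher z scale is 1/√39 = 0.16, about four times as large.

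**Effect on the group comparison.** Take n = 42, a three-group ANOVA, and a marker correlated with the noise-free time-weighted mean, a set-up that favours time-weighting. Power with plain against time-weighted grouping is 29.8% against 30.3% at r = 0.3, and 75.7% against 76.6% at r = 0.5. Over the assumed range of day systolic pressure and SD the difference runs from −0.2 to +1.7 percentage points.

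**Cost of time-weighting.** The standard error of a patient's mean is 12 × √(1/40) = 1.90 mmHg plain and 12 × √((2/3)²/32 + (1/3)²/8) = 2.00 mmHg time-weighted, a ratio of 1.054. Correlation with the dip is −0.11 to −0.16 for the plain mean and −0.18 to −0.25 for the time-weighted one, so time-weighting makes the grouping more dip-related.

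**The case for a change.** The strongest case for a change is that the gap is real and cheap to close. The averaging rule appears in neither document, the two readings of the word differ in a direction tied to a hypothesised pattern, and two or three patients of 42 depend on the choice. If the time-weighted mean is the target, plain averaging places 7.5% to 10.2% of patients in the wrong group, against 5.8% to 7.8% with time-weighting (reading SD 12). It also errs upwards more often than downwards, 5.6%–7.5% against 1.9%–2.7%. One sentence and a recalculation from stored readings would settle it.

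The gap and the arithmetic stand. The misclassification figures do not carry the argument, because they take the time-weighted mean as truth. The protocol does not say which mean its 130 and 140 cut-points refer to, so only the share of patients who change group is neutral between the two rules. Even on the favourable assumption, the net gain is 1.7 to 2.4 percentage points, or 0.7 to 1.0 patient of 42. With no average dip, the case closest to the protocol's remark on non-dippers, it falls to 0.3 to 1.5 points, or 0.1 to 0.6 of a patient. The dipping argument does not favour time-weighting either, since that mean is the more dip-related of the two. Finally, the protocol gives the study period as "Date. abril 2023– junio 2024" and both documents are dated 09/11/2025. Collection therefore appears complete, and prescribing a new main definition now would be post hoc if results are known.

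**Conclusion.** No change to the plan follows. The wording leaves the averaging rule open, but nothing in either document conflicts with a plain mean or with a time-weighted one, and an analyst using either would reach sound conclusions. The two differ by about 1 mmHg on average at a 5% dip and by under 2 mmHg at a 10% dip. They place about 5% to 7% of patients in different groups and leave correlations and ANOVA power practically the same. Time-weighting has a small cost of its own: a standard error about 5% larger and a closer tie to dipping. A report that names the mean used covers the gap.

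These sizes rest on assumed hours in bed, pressure distribution, dip and reading noise, with no readings lost. The size of the shift does not depend much on the recording window: over 44 or 68 hours, with 14–16 or 20–24 bed hours assumed, the multiplier is 0.122 to 0.141 against 0.133 for 24 hours. A much larger average dip would move more patients between groups, but the protocol's own expectation of frequent non-dipping points the other way.

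### Patients on unchanged glucocorticoids or immunosuppressants are eligible and the inflammation–pressure analyses are unadjusted, so the association can be partly a drug effect or be masked by one; the size is unknown

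*Protocol*

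**What the plan says.** **Eligibility.** The Protocol's inclusion criteria ask for "Stable clinical conditions with no evidence of infection or treatment changes in the previous month". The exclusion criterion nearest to concurrent medication is "Participation of the patient in another clinical trial requiring interventional treatment". None of the six exclusions names glucocorticoids, immunosuppressants, or inflammatory or autoimmune disease. Under Therapy the Protocol adds: "Treatment received by the patient will not be modified".

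**Measures.** Inflammation is measured by TNF-alpha ("Human TNF-alpha Quantikine HS ELISA, R&D systems, Cat.# HSTA00E") and by a white-cell ratio: "Peripheral white cell counts were used to calculate the NMLR (neutrophils + monocytes /lymphocytes ratio) inflammation index".

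**Question.** The primary outcome relates ambulatory pressure to "the interdialytic weight gain and the levels of angiotensin II and inflammatory markers in patients in chronic dialysis". The working hypothesis is mechanistic: the renin-angiotensin system and "the inflammatory reactivity play a critical role in the severity of hypertension". The Background adds: "If these findings are shown in dialysis patients it is possible that anti-inflammatory treatment could have anti-hypertensive effects".

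**Analysis.** The Protocol's Statistical Analysis section plans t tests, ANOVA or Kruskal-Wallis tests, and Pearson or Spearman correlations, at two-sided 0.05. The SAP lists group comparisons only. Neither document has a regression model, a covariate, a stratified or sensitivity analysis by medication, or a statement that these drugs will be recorded.

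**The concern.** A month without treatment changes removes recent changes. It does not remove a lasting difference between patients who take a drug and patients who do not. If glucocorticoid users have a higher neutrophil-to-lymphocyte balance and a higher pressure because of the drug, NMLR and pressure will correlate across the cohort even when inflammation plays no part. If an immunosuppressant lowers TNF-alpha in patients whose pressure is raised, a true positive association shrinks.

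Inflammation is one of the three predictors in the primary outcome, and the hypothesis reads the association as a mechanism. With only unadjusted correlations and group tests, a reader of the results could not tell a drug pattern from an inflammatory one.

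**Working it through.** The plan has no power or effect-size calculation to reproduce. The 40–45 patients under Recruitment potential are an expected head count; n = 42 is used here.

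**Inputs.** From the documents: n of about 42 and a two-sided 0.05 test. Assumed, because the documents give none: the share of users p (5%, 15%, 25%, or about 2, 6 and 10 of 42), the marker shift in users a, and the systolic pressure shift in users b, both in within-group SD. Normal data and the Pearson test are assumed, with NMLR on a log scale.

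**1. Correlation created by the drug alone (no true link).**

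r = p(1−p)ab / √[(1 + p(1−p)a²)(1 + p(1−p)b²)]

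- p = 0.05, a = 1.0, b = 0.5: 0.0475 × 0.5 / √(1.0475 × 1.0119) = 0.0238 / 1.0295 = 0.02
- p = 0.15, a = 1.0, b = 0.5: 0.1275 × 0.5 / √(1.1275 × 1.0319) = 0.0638 / 1.0786 = 0.06
- p = 0.25, a = 1.5, b = 0.75: 0.1875 × 1.125 / √(1.4219 × 1.1055) = 0.2109 / 1.2537 = 0.17

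The critical |r| at n = 42 is 2.021 / √(40 + 2.021²) = 0.304. The induced correlation stays below it, but it moves the centre of the sampling distribution and so raises the rejection rate.

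**2. False-positive rate** (20,000 simulated studies per scenario, a = 1.0 to 1.5, b = 0.5 to 0.75):

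| Users | Unadjusted | Adjusted for use |
|---|---|---|
| 5% | about 5–6% | about 5% |
| 15% | 7–12% | about 5% |
| 25% | 8–19% | about 5% |

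A wider assumed grid (10–30% use, a = 0.5 to 1.5, b = 0.5 to 1.0, n = 40 and 45) gives about 5% to 37% unadjusted. The top value needs 30% use with the largest shifts in both variables.

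**3. Masking.** Take a true r of 0.40, with users' TNF-alpha 1 SD lower and systolic pressure 0.5 SD higher. The expected correlation is (0.40 − 0.5p(1−p)) / √[(1 + p(1−p))(1 + 0.25p(1−p))].

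- 15% use: (0.40 − 0.0638) / 1.0786 = 0.31; simulated power 53%, against about 75% adjusted.
- 25% use: (0.40 − 0.0938) / 1.1150 = 0.27; simulated power about 42%, against about 75% adjusted.

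**4. One drug indicator or two?** The adjusted column in step 2 assumes that every user has the same shift. Suppose instead that half of the users have marker +1.5 SD and pressure +0.75 SD, and the other half have marker −1.0 SD and no pressure shift. The false-positive rates at n = 42 are then:

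| Users | Unadjusted | One pooled yes/no | Two separate indicators |
|---|---|---|---|
| 15% | 7.5% | 6.4% | about 5% |
| 25% | 10.5% | 8.7% | about 5% |

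Of the excess over 5%, the pooled indicator leaves 1.4 of 2.5 points and 3.7 of 5.5 points, more than half in each case.

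**5. Precision without users.** Power for a true r of 0.40 is about 76% at n = 42, about 69% at 42 − 6 = 36, and about 63–64% at 42 − 10 = 32.

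**The case against.** The strongest reply is that the size rests wholly on assumptions. The documents give no usage rate, no comorbidity mix and no drug effect, and the pharmacology is general knowledge. At 5% use the inflation is negligible, and rates of 12–19% need 15–25% use together with large shifts in both marker and pressure. The study is exploratory, and the root gap is wider: no adjustment is planned for any confounder. All of this stands. It limits how large the problem can be said to be. It does not remove the two documented facts, eligibility and unadjusted analysis, and an unknown usage rate is itself a reason to record it.

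A further objection concerns over-correction. These drugs may be prescribed because of inflammatory disease, so adjusting for them or dropping users can remove real inflammatory variation. A rule that an association must be significant in non-users would also cost power (step 5). Both points stand, and the fix avoids such a rule.

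Three stronger readings are tempting and are not supported:

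- **That the stability rule was written to protect the inflammatory markers and fails at it.** The Protocol gives no reason for the rule; it serves pressure and weight gain equally well.
- **That the two markers are biased in opposite directions.** This joins a glucocorticoid effect on NMLR to an immunosuppressant effect on TNF-alpha. These are different drugs, possibly in different patients, and nothing in the documents shows it for this cohort.
- **That a positive result would lead to a treatment recommendation.** The Background speaks only of a possibility and rests it also on experimental and patient data.

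**Conclusion.** The concern holds as a possibility created by the design. Patients on stable glucocorticoids or immunosuppressants can enter, and nothing in the planned analyses separates them, so an inflammation–pressure association can be partly a drug effect or be masked by one. The documents do not show that it will be, nor in which direction.

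The size is unknown. On the main assumptions the false-positive rate runs from about 5% (no real harm) at 5% use to 19% at 25% use with the larger shifts, and a true correlation of 0.40 could appear as 0.31 or 0.27. The problem is negligible if few patients take these drugs and material if about a fifth do and the shifts are near 1 SD or more. Every figure depends on the assumed p, a and b.

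**What to change.** - Take from the chart, as of the time of the blood sample, two separate yes/no variables: systemic glucocorticoid use, and other immunosuppressant use. Report both by blood-pressure group.
- Keep the planned correlations. Beside them, report TNF-alpha and NMLR against ambulatory pressure adjusted for the two indicators, by partial correlation or regression.
- As a sensitivity analysis, give the estimate with its 95% confidence interval in non-users.
- Interpret an association as inflammatory only with these estimates shown and broadly consistent in direction and size. Do not require p < 0.05 in non-users.

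The Protocol's stated study period (April 2023 to June 2024) precedes the document date, so a chart-based remedy is the practical one. No patient's eligibility or treatment changes.

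The cost is two chart variables, up to two degrees of freedom, and a non-user estimate that is less precise and may leave out patients with inflammatory disease. If use turns out to be rare, one line in the report settles the matter.

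### The exclusion criterion for incomplete data has no stated scope; read literally, it is a post-enrolment complete-case rule that can discard usable primary-outcome data

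*Protocol*

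**What the plan says.** The protocol's Exclusion Criteria contain the line "Incomplete collection of data". No variable, threshold, time point or analysis is attached to it. Two neighbouring lines deal with specific losses: "Incapacity of placement of ABPM or insufficient valid recordings" and "Voluntary withdrawing of informed consent".

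The Primary Outcome relates interdialytic blood pressure by ABPM to "the interdialytic weight gain and the levels of angiotensin II and inflammatory markers". Cardiac output and systemic vascular resistance are named as outcome variables only in secondary outcome 2.

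The measurements are made at different times. Under Methods, General, the ultrasound is scheduled as "1-2 hours after the end of dialysis the determination of cardiac output and central venous pressure determinations", while the draw for the biomarkers is at the other end of the interval: "Blood samples (10 ml) will be taken at the end of the interdialytic period, (prior to the next dialysis) for the biomarkers under study". The laboratory section adds that "Peripheral white cell counts were used to calculate the NMLR" inflammation index, without saying whether those counts come from the same draw.

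The protocol's Statistical Analysis section and the SAP choose tests and a significance level. Neither defines an analysis set or says what happens to a patient with a missing value. Retirement of participants requires the cause to be recorded, but describes retirement as arising from patient request, fever or an adverse event, not from a missed measurement. Recruitment potential estimates 40-45 patients out of 50-55 in the programme.

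**The concern.** Completeness of data can be known only after a patient has been enrolled and measured. Placed among the exclusion criteria with no limit, the line works as a complete-case rule for the whole study, although it is not presented as one.

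Three things follow. A patient with usable primary-outcome data could be lost because of an item that the primary outcome does not use. Two analysts could form different analysis sets from the same records, because the text does not define what counts as incomplete. And patients removed this way need not appear in the retirement record. In a single-centre cohort drawn from 50-55 people, a patient lost like this cannot easily be replaced.

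**Working it through.** **Does anything narrow the line?** ABPM failure and consent withdrawal have their own lines, so unless this one is redundant it reaches other data. Those could be weight, blood results or ultrasound; the text does not say. Bioimpedance does not settle the scope. It was dropped for the whole study (Abstract note; Methods, Biometric Bioimpedance), which does not show what happens when one patient misses a retained item. Because ultrasound and blood sampling occur at different times, one can be missed without the other.

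**Inputs.** The 40-45 is a feasibility count. The protocol gives no effect size, power or dropout rate, so there is no sample-size calculation to reproduce. I take n = 42 within that range and the two-sided 0.05 level from the plan. The 80% power is my choice for illustration. Every missing rate below is an assumption, since the documents give none.

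**Formula.** Detectable correlation (Fisher z approximation): r = tanh((1.960 + 0.842)/√(n − 3)). At n = 42: tanh(2.802/√39) = 0.421.

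**Scenario 1: only the ultrasound is missed.** Patients with complete primary data who are lost = n × p.

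| Assumed rate p | Lost of 42 | n left | Detectable r |
|---|---|---|---|
| 0 | 0 | 42 | 0.421 |
| 5% | 2.1 | 40 | 0.431 |
| 10% | 4.2 | 38 | 0.441 |
| 20% | 8.4 | 34 | 0.465 |

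For n = 40 to 45 the losses are 2.0-2.3, 4.0-4.5 and 8.0-9.0. The 20% row is a wide upper limit, since the protocol's Risks section describes ultrasound as routine in these patients.

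**Scenario 2: every collection event is missed at the same rate, independently.** With k primary events, the primary-complete patients lost because of the ultrasound = 42 × (1 − p)^k × p. Here k = 3 (ABPM, weight, blood), or k = 4 if the white-cell count is a separate event.

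| p | k = 3 | k = 4 |
|---|---|---|
| 2% | 0.8 | 0.8 |
| 5% | 1.8 | 1.7 |
| 10% | 3.1 | 2.8 |

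At 5%, k = 3 takes n from 36.0 to 34.2 (r 0.452 to 0.465); k = 4 takes it from 34.2 to 32.5 (about 34 to 32; r 0.465 to 0.478).

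**Scenario 3: same assumptions, one two-variable correlation.** A correlation of ABPM pressure with angiotensin II needs two events (ABPM and blood). The literal rule needs all four (those two, weight and ultrasound). Patients lost = 42 × [(1 − p)² − (1 − p)⁴].

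- 2%: 42 × (0.9604 − 0.9224) = 1.6.
- 5%: 42 × (0.9025 − 0.8145) = 3.7; n from 37.9 to 34.2, r 0.441 to 0.465.
- 10%: 42 × (0.8100 − 0.6561) = 6.5; n from 34.0 to 27.6, r 0.465 to tanh(2.802/√25) = 0.508.

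**The case against.** The strongest reply is that an undefined scope cuts both ways. A reader might infer that the protocol definitely removes anyone without an ultrasound. It does not say so. The line is never tied to ultrasound, and the investigators may have meant only the weight and blood data that the primary outcome needs. That stands: removal is the literal reading, not a certainty. What remains is that the text does not let a reader tell which rule was applied.

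A reader might also infer that patients have already been lost, or that the results are biased. Neither is supported. No exclusion under this line is reported, and nothing shows that missingness is related to blood pressure.

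The arithmetic can be challenged too. Scenarios 2 and 3 treat misses as independent. If the patients who miss ultrasound are mostly those who also lack primary data, the loss falls below the figures shown. The estimate of 40-45 may already allow for this exclusion; the documents do not say. The plan also sets no power target that these shifts could breach, since it invites every eligible patient. All of this stands, and it limits the size of the point.

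Finally, the stated study period ended in June 2024 and the documents are dated 2025, so deleting a criterion now is a change made after data collection. That is a reason to label the change, not to leave the rule undefined.

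**Conclusion.** The point holds as a minor one. The exclusion line has no stated scope and nothing else in either document limits it. Its literal effect is a complete-case rule that could remove usable primary data over an unrelated item.

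The effect on precision is modest. If 5% to 10% of 42 patients miss only the ultrasound, detectable r moves by 0.010 to 0.020. With a 5% miss rate at every event, a two-variable correlation loses about 4 patients (0.024 in r). Larger losses need about one miss in ten at every event, or one in five at the ultrasound, and the documents give no support for either. These sizes rest on assumed rates, on independence in the equal-rate scenarios, and on 42 being the number before any such exclusion.

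**What to change.** - Remove the incomplete-data line from the exclusion criteria. Leave the ABPM and consent-withdrawal lines as they are.
- State in the SAP that each analysis includes every eligible patient with valid ABPM (where the analysis uses it) and the specific variables it needs. Each correlation of blood pressure with a marker then requires only its own two variables. Requiring the full set of primary variables for every correlation would repeat the same fault on a smaller scale.
- Restrict only the comparison of mechanisms with each other (the relative-importance question under Hypothesis and research questions) to patients with all of the variables compared.
- Report n for each analysis and the number missing for each variable, with reasons.
- State whether any patient was excluded on this ground alone. If so, include them in the analyses for which they have data, and label this as a change made after data collection.

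The cost is a few sentences in the protocol and SAP and one missing-data table. The drawback is that denominators, and so the patients analysed, will differ slightly between analyses; using a common set for the comparison of mechanisms limits this where it matters most.
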